Title: Dietary Management of Gestational Diabetes Mellitus

NCT ID not yet assigned

Document date: 2021.11.23

Study protocol

Participants

The target population was selected from 48 patients with gestational diabetes mellitus attending the obstetrics outpatient clinic of the Affiliated Hospital of XXX. The study objects were selected by non synchronous control, for example, patients who visited the hospital in the first week were included in the control group, and patients who visited the hospital in the second week were included in the experimental group until saturation.

Intervention

The intervention group

The intervention group received a 12-week dietary management intervention based on the nudge strategy. The MINDSPACE framework was used, which has nine intervention categories. Face-to-face intervention and telephone follow-up were used to provide targeted dietary management.

The control group

During the intervention, patients in the control group received routine obstetric health education and instruction under contamination, but no additional information on dietary management based on nudge strategies.

Statistical analysis plan

Data collection

From October 21, 2022 to December 31, 2022 (prospective), data was collected. At the time of enrollment, demographic information about the study participants was gathered. Pre-intervention, 1-month post-intervention and 3-months post-intervention, patients' glucose level indicators (FPG, 2hPG) and pregnancy outcomes were collected. The study subjects had no knowledge of group assignments.

Statistical analysis

All statistical analyses were carried out using SPSS, version 26.0 (SPSS Inc., Chicago, IL, USA). Continuous variables with normal distributions were expressed as $x \pm s$ and compared between groups using the independent samples t-test; continuous variables with non-normal distributions were expressed as M (Q1, Q3) and compared

between groups using the Wilcoxon rank sum test; categorical variables were expressed as cases (%) and compared between groups using χ^2 test and categorical variables were described as percentages and compared using chi-square test. Metrics that are repeated the time effect, the main effect of the intervention, and the interaction effect of both FBG and 2hPG before, 1 month after, and 3 months after the intervention were all compared in the two groups using ANOVA. $P < 0.05$ with two tailed significance was considered statistically significant.

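### Allocation by week of visit lets staff know a woman's group before enrolling her and ties group to calendar period; the planned tests offset this only in part

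*Combined protocol and SAP*

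**What the plan says.** Study protocol, Participants, sets out the allocation rule: "The study objects were selected by non synchronous control". The section illustrates this with two clinic weeks. For the earlier week it says that "patients who visited the hospital in the first week were included in the control group". Women attending a week later go to the other arm, and recruitment runs on until saturation is reached. The total is 48 women, and the split between groups is not stated. The section gives no random sequence, no concealment, no requirement to enrol every eligible woman in turn and no screening log. Because the weeks are given as an example, it is unclear whether they keep alternating or each group is a single block.

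The only masking statement is under Statistical analysis plan, Data collection: "The study subjects had no knowledge of group assignments". Nothing is said about the staff who recruit.

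Under Statistical analysis, normally distributed variables are "compared between groups using the independent samples t-test". Non-normal variables get a Wilcoxon rank sum test and categorical variables a chi-square test. Repeated glucose measures go into an ANOVA that tests time, group and "the interaction effect of both FBG and 2hPG before, 1 month after, and 3 months after the intervention". No analysis includes a baseline covariate or a term for week. The two-sided significance level is 0.05.

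**The concern.** Two separate problems follow from the allocation rule.

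- **Foreknowledge.** Anyone who knows the current week's group knows a woman's assignment before approaching her. Who is approached, judged eligible or encouraged to join can then differ between groups. Masking the women does not prevent this, because the decision comes before they are enrolled.
- **Calendar period.** Group and week coincide. With one block per group, anything that changes over time (referral mix, clinic staff, season, laboratory) cannot be separated from the intervention. Alternating weeks would lessen a slow trend, but the group would still be predictable.

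At stake is whether a difference in FPG, 2hPG or pregnancy outcomes can be attributed to the dietary programme, or partly reflects who was enrolled when.

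**Working it through.** The plan gives no effect size, SD, correlation or bias estimate, so it has no figure to reproduce. The check asks how often each test would be significant with no true effect if the allocation produced a modest group difference.

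**From the plan:** 48 women; three visits (before, 1 month, 3 months); two-sided 0.05.

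**Assumed:** 24 per group; SD 1 at each visit; correlation 0.5 between any two visits; no intervention effect; a group difference *d*, shown for *d* = 0.3 SD and then for 0.2 and 0.5.

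**Three forms of difference**
- (a) *d* at baseline, regressing to 0.5*d* at both follow-up visits.
- (b) *d* at all three visits.
- (c) Zero at baseline, *d* at both follow-up visits.

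**Standard errors of the group difference**
- 3-month t-test: √(2/24) = 0.289.
- ANOVA group main effect: a woman's three-visit mean has variance (1 + 2×0.5)/3 = 0.667, so SE = √0.667 × 0.289 = 0.236.
- 3-month ANCOVA on baseline: residual variance 1 − 0.5² = 0.75, so SE = √0.75 × 0.289 = 0.250.

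**Bias at *d* = 0.3**
- Main effect: (a) (0.30 + 0.15 + 0.15)/3 = 0.20; (b) 0.30; (c) (0 + 0.30 + 0.30)/3 = 0.20.
- t-test: (a) 0.15; (b) 0.30; (c) 0.30.
- ANCOVA (3-month difference minus 0.5 × baseline difference): (a) 0.15 − 0.15 = 0; (b) 0.30 − 0.15 = 0.15; (c) 0.30 − 0 = 0.30.

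**False-positive rate,** normal approximation: Φ(bias/SE − 1.96) + Φ(−bias/SE − 1.96). For the main effect in (b), 0.30/0.236 = 1.27, which gives 24.7%. For ANCOVA in (b), 0.15/0.25 = 0.6, which gives 9.2%. Simulation, which uses the exact t and F references, gives slightly lower figures. The interaction F test (2 and 92 df) was obtained by simulation only.

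| Scenario (simulated) | ANOVA main effect | 3-month t-test | Group × time | ANCOVA |
|---|---|---|---|---|
| No difference | 4.9% | 4.9% | 4.8% | 5.0% |
| (a) *d* = 0.2 | 8.4% | 6.5% | 6.1% | 4.9% |
| (a) *d* = 0.3 | 13.2% | 7.9% | 7.7% | 4.9% |
| (a) *d* = 0.5 | 28.1% | 13.4% | 13.4% | 5.0% |
| (b) *d* = 0.2 | 13.2% | 10.5% | 5.0% | 6.7% |
| (b) *d* = 0.3 | 24.0% | 17.4% | 5.0% | 9.1% |
| (b) *d* = 0.5 | 54.8% | 39.9% | 4.9% | 15.5% |
| (c) *d* = 0.3 | about 13% | about 17% | about 17% | 21 to 22% |

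Rows other than (c) use 40,000 simulated trials each. Row (c) summarises separate smaller runs that agreed closely. At *d* = 0.5 in (c), the planned tests gave 29.3% (main effect), 40.7% (t-test) and 40.0% (interaction).

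The interaction holds 5% only in (b). ANCOVA holds 5% only in (a). Nothing holds it in (c).

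**Clustering by week (secondary).** Design effect = 1 + (m − 1) × ICC, and actual size = 2 × [1 − Φ(1.96/√DE)]. With an assumed ICC of 0.02:
- m = 4.8 (48 women over an assumed 10 weeks): 1 + 3.8×0.02 = 1.08, size 5.9%.
- m = 24 (one week per group): 1 + 23×0.02 = 1.46, size 10.5%.

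**The case against.** - **The design is declared openly.** The plan never claims randomisation. Separating groups by week is a recognised way to limit contamination in a one-clinic behavioural study, and the control-group text mentions contamination. This stands as a reason to consider weekly blocks, but not for a predictable, unconcealed sequence.
- **Selection is possible, not shown.** This is correct. The documents do not show that staff acted on their knowledge, and complete period confounding depends on there being one block per group. The weakness lies in having no safeguard.
- **The sizes are assumed.** Also correct: shifts of 0.2 to 0.5 SD, correlation 0.5, equal groups and the ICC have no source in the plan. ANCOVA's 5% in (a) follows by construction, because the shift regresses by exactly the assumed correlation. The table shows direction and rough size only.
- **A 3-month t-test may not be intended for glucose.** The plan sends repeated glucose measures to ANOVA, so the t-test column may not describe a planned glucose analysis. The main effect, which is explicitly planned, does worse than the t-test in (a) and (b).
- **ANCOVA is not always better.** Under (b) the planned interaction holds 5% and ANCOVA does not. Baseline adjustment is therefore a sound choice once allocation is random and concealed. For week-based data already allocated, it should be shown beside the interaction rather than replace it.

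**Conclusion.** The concern holds. Foreknowledge of group and the link between group and period follow directly from the stated rule, and masking the participants covers neither. The planned interaction does real work against a stable baseline glucose difference. It does not remove a difference that arises after baseline, and it offers nothing for pregnancy outcomes.

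Under the stated assumptions, a 0.3 SD difference raises the 5% error rate of the ANOVA main effect to between about 13% and 24%, and that of the interaction to as much as about 17%, depending on the form the difference takes. Clustering by week is a lesser matter, since neither the ICC nor the number of weeks is given. The structural conclusion does not depend on the assumed sizes: with no single analysis protecting in every scenario, the protection has to come from the allocation. This must be fixed before group differences are read as effects of the programme.

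**What to change.** **Preferred.** Assign women individually from a computer-generated list with varying block sizes, in sealed opaque envelopes opened only after consent and baseline glucose measurement. The cost is a list and envelopes for 48 women. The drawback is some possible contamination between groups in one clinic.

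**If weekly blocks are kept to limit contamination:**
- randomise the order of several weeks, without fixed pairs;
- have the sequence held by someone who does not recruit;
- have eligibility, consent and enrolment of every consecutive eligible woman settled by staff unaware of that week's group;
- log everyone screened;
- account for week in the analysis with a small-sample degrees-of-freedom correction, which is impossible with one week per group.

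This costs extra staffing, several weeks per group and some precision.

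**Under either option,** compare post-baseline FPG and 2hPG adjusted for the baseline value, instead of relying on the ANOVA main effect. This needs only SAP wording and uses data already collected.

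**If week-based allocation has already been used,** describe the study as non-randomised, state how many weeks each group covered, report the baseline-adjusted analysis alongside the group-by-time interaction, and limit causal conclusions, above all for pregnancy outcomes.

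### Arm is set by the week of any clinic visit, with no qualifying visit and no rule for women seen in both weeks, so imbalance in visit frequency or time since diagnosis is possible and uncorrected.

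*Combined protocol and SAP*

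**What the plan says.** Under Study protocol, Participants, the sample is "selected from 48 patients with gestational diabetes mellitus attending the obstetrics outpatient clinic". The section sets no criterion on time since diagnosis, gestational age or earlier management.

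Allocation is introduced by "The study objects were selected by non synchronous control, for example". The example has one part for each arm. For the control arm it reads "patients who visited the hospital in the first week were included in the control group". The part for the other arm, which carries no exclusion of women already seen, reads "patients who visited the hospital in the second week were included in the experimental group until saturation". Neither part names a first visit, a diagnosis date or a tie-break.

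Under Data collection, the only entry data listed besides the pre-intervention glucose values and pregnancy outcomes are demographic: "At the time of enrollment, demographic information about the study participants was gathered". Under Statistical analysis, the groups are compared by t-test, rank sum test or chi-square test, and FPG and 2hPG by repeated-measures ANOVA with time, group and interaction effects. No covariate is named.

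**The concern.** Read literally, a woman who attends in both weeks meets both rules, so the text does not define one arm per participant. Someone at the clinic has to settle it, and the document does not say how.

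How it is settled affects who ends up in each arm. Suppose a woman takes the arm of her first visit in the study. Everyone in the existing clinic population who attends weekly is then absorbed in the first (control) week. The second week receives the less frequent attenders and women diagnosed since. Visit frequency and time since diagnosis are plausibly related to gestation, severity and how much of the glucose fall under routine care has already happened. If the experimental arm holds more recently diagnosed women, their glucose may fall further whatever the intervention does. That would show up as a group-by-time interaction, which is one of the effects the plan tests. This route needs no selection by staff and no calendar trend, so it is separate from the general weakness of a non-randomised, non-concurrent control.

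**Working it through.** The plan gives no figure to reproduce: 48 is its only size, and it states no visit frequency and no mix of new and known cases. Every input below except the alpha of 0.05 is therefore an assumption.

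**1. Overlap and frequent attenders, two-week example.** Let a share w of the clinic population attend weekly and the rest at fixed fortnightly intervals, with the first match counting. Week 1 takes w + (1 − w)/2 and week 2 takes the other (1 − w)/2. The weekly attenders' share of control is w / [w + (1 − w)/2], and their share of the experimental arm is 0.

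| w | weekly attenders, control | weekly attenders, experimental |
|---|---|---|
| 0 | 0% | 0% |
| 0.2 | 0.2/0.6 = 33% | 0% |
| 0.3 | 0.3/0.65 = 46% | 0% |
| 0.4 | 0.4/0.7 = 57% | 0% |

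The share of the population meeting both rules is w. If both-week women are placed in the experimental arm instead, the two columns swap.

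**2. Women already diagnosed.** Add new diagnoses each week equal to 15% of the existing population, each counted once.
- w = 0: control 0.5/0.65 = 77%, experimental 0.5/0.65 = 77%. Difference 0.
- w = 0.1: control 0.55/0.70 = 79%, experimental 0.45/0.60 = 75%. Difference 3.6 points.
- w = 0.3: control 0.65/0.80 = 81%, experimental 0.35/0.50 = 70%. Difference 11 points.

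Fixed intervals matter for the null result. If non-weekly women attend at random with probability 0.5 each week, overlap arises even at w = 0. With 5% new cases, 0.25/0.55 = 45% of week-1 women are seen again in week 2, and known cases are 91% v 83%.

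**3. Effect on 1-month change.** Assume routine care lowers glucose by D = 1 SD after diagnosis with a 2-week half-life (k = ln 2 / 2 = 0.347 per week). The fall over 4.35 weeks, starting t weeks after diagnosis, is D[exp(−kt) − exp(−k(t + 4.35))].
- New case (t = 0): 1 − exp(−1.51) = 0.78 SD.
- Known case, t spread evenly over 0 to 10 weeks: the mean of exp(−kt) is (1 − exp(−3.47))/3.47 = 0.28, so 0.78 × 0.28 = 0.22 SD.
- Gap: 0.78 − 0.22 = 0.56 SD.

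Spurious difference = difference in share × 0.56:
- 0 points gives 0.
- 3.6 points gives 0.02 SD.
- 11 points gives 0.06 SD.
- 30 points gives 0.17 SD.

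Two simulations of weeks alternating until 24 per arm (populations of 20 to 40, 3 to 5 new cases a week, 1 SD fall, 2-week half-life, first match counting) gave 0.01–0.15 SD and 0.05–0.18 SD towards the intervention. Both assumed that some women attend weekly, so neither range contains the null case.

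The top of the range is not a ceiling. The most lopsided two-week inputs tried (half the women weekly, the rest attending at random about every four weeks, 15% new) give 81% v 38% known cases, or 0.42 × 0.56 = 0.24 SD.

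**4. Effect on type I error.** With 24 per arm (an equal split of 48) and the SD of change as the unit, SE = √(2/24) = 0.289 SD. For a bias b, the two-sided error is Φ(b/SE − 1.96) + Φ(−b/SE − 1.96).
- b = 0: 5.0%.
- b = 0.05: b/SE = 0.17, giving 5.3%.
- b = 0.15: b/SE = 0.52, giving 8.1%.
- b = 0.18: b/SE = 0.62, giving 9.6%.

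**The case against.** The strongest reply is that the overlap depends on a very literal reading. The rule is offered as an example and may not be the full operating rule. The plan refers to a single time of enrolment, so a woman already included in week 1 would ordinarily not be included again. This has force against any suggestion that women were counted twice, which the documents do not support. It does not supply the missing rule. A woman seen in both weeks still has no stated arm, and if enrolment at first contact is what is meant, that is the assignment that can enrich the control week.

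A reader might also infer that the control week does collect frequent attenders and already-managed women, so that the result is biased towards the intervention. The documents do not support that. It needs three things they do not state: some women attending more often than the weeks alternate (or irregularly), known cases being enrolled, and the first match counting. With fixed 2- or 4-weekly visits and no weekly attenders there is no overlap and no imbalance. If both-week women go to the experimental group, the direction reverses.

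Two further objections stand. Even under unfavourable assumptions the bias is modest beside an SE of 0.29 SD. And random allocation of individuals would make the point moot, so it is secondary to the openly declared non-random design.

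**Conclusion.** The gap in the text is real: arm depends on the week of any visit, no qualifying visit is defined, and no rule covers women seen in both weeks. Imbalance in visit frequency or time since diagnosis is therefore possible and cannot be excluded. It is not shown to exist, and its direction is not fixed.

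The illustrative size is about 0 to 0.18 SD in the 1-month change. It rests on assumed attendance patterns, rates of new diagnosis, a 1 SD fall and a 2-week half-life. The type I error figures also assume 24 per arm.

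The planned analysis has no covariate that would correct an imbalance, and time since diagnosis is not listed among the data collected. Baseline glucose is collected but not used for adjustment. It records a woman's level at entry, not how much of her fall is still to come, so it may not be enough alone; that was not quantified. Rating: should-fix, because the remedy is cheap but the harm is conditional and modest.

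**What to change.** **Allocation.** Define one index visit per woman: her first clinic visit with gestational diabetes after recruitment opens. Set the arm by the week of that visit, and keep it for follow-up and analysis whatever week she later attends.

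**Data and analysis.** The index visit makes the arms mutually exclusive, but it is itself a first-match rule, so it does not prevent the sorting. Record date of diagnosis, gestational age and prior management at entry. Adjust the FPG and 2hPG comparisons for time since diagnosis, gestational age and baseline glucose. The adjustment must act on the change over time, for example by modelling the 1- and 3-month values with these covariates. A covariate entered only as a between-woman main effect would leave the group-by-time interaction uncorrected.

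**Optional.** Restricting entry to newly diagnosed women removes the sorting more fully, but it changes the trial population and slows recruitment. At an assumed 3 to 5 new cases a week, 48 women take 48/5 = 9.6 to 48/3 = 16 weeks. The stated collection window, 21 October to 31 December 2022, is 72 days (72/7 = 10.3 weeks) and must also hold follow-up.

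**Cost.** One sentence in Participants, a few data fields, and three covariates. In a two-group comparison of 48 women that reduces the residual degrees of freedom from 46 to 43. Some imbalance in visit frequency may remain after adjustment and should be acknowledged as a limitation.

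### The stated data-collection window (21 Oct to 31 Dec 2022, 71 days) is shorter than the 12-week intervention, so it can hold no 3-month measurement

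*Combined protocol and SAP*

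**What the plan says.** Three statements in the combined protocol and SAP bear on timing.

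- Under Data collection, the window is given as calendar dates: "From October 21, 2022 to December 31, 2022 (prospective), data was collected". The next sentence puts enrolment data under the same heading: "At the time of enrollment, demographic information about the study participants was gathered".
- Under The intervention group, the duration is given: "The intervention group received a 12-week dietary management intervention based on the nudge strategy".
- Under Data collection, the visits are listed: "Pre-intervention, 1-month post-intervention and 3-months post-intervention, patients' glucose level indicators (FPG, 2hPG) and pregnancy outcomes were collected".

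Under Statistical analysis, the only longitudinal comparison uses all three glucose time points. It is an ANOVA with terms for group, time and their interaction; the sentence that sets it out includes the words "interaction effect of both FBG and 2hPG before, 1 month after, and 3 months after the intervention were all compared in the two groups using".

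Under Participants, entry is staggered by calendar week. In the plan's example, controls come from the first week, and "patients who visited the hospital in the second week were included in the experimental group until saturation".

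No separate recruitment period, follow-up period or date of last visit appears anywhere in the document.

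**The concern.** A period described as the time when data were collected has to contain every planned measurement. This one ends before even the earliest participant could complete the intervention. If data collection closed on the stated date, FPG and 2hPG at 3 months would be missing for everyone in both groups. The three-level time effect and the group-by-time interaction could then not be estimated. A conventional repeated-measures ANOVA uses complete cases, and there would be none.

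Pregnancy outcomes would also be truncated for women who had not delivered by 31 December. The extent of that cannot be sized, because the plan gives no gestational age at entry and does not define the outcomes.

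If 3-month results are reported anyway, a reader cannot reconcile them with the stated dates. Nothing would show whether the dates were wrong, the intervention was shortened or the visit was moved.

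**Working it through.** **Inputs, all from the document**

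- Window: 21 October 2022 to 31 December 2022 (Data collection).
- Intervention: 12 weeks (The intervention group).
- Visits: before the intervention, at 1 month and at 3 months (Data collection).
- Sample: 48 women (Participants).

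The document states no length for the window, so there is no figure of its own to reproduce first.

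**Length of the window**

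31 Dec 2022 − 21 Oct 2022 = 10 days (rest of October) + 30 + 31 = 71 days, or 72 counting both end dates. 71 / 7 = 10.1 weeks.

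The intervention takes 12 × 7 = 84 days. Shortfall: 84 − 71 = 13 days.

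**Best case: a woman enrolled on the first day, 21 October 2022**

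| Event | Date | Days after 31 Dec 2022 |
|---|---|---|
| 12 weeks completed (21 Oct + 84 days) | 13 Jan 2023 | 13 |
| 3 calendar months from start (92 days) | 21 Jan 2023 | 92 − 71 = 21 |
| 1 month after the intervention ends | 13 Feb 2023 | 31 + 13 = 44 |
| 3 months after the intervention ends | 13 Apr 2023 | 31 + 28 + 31 + 13 = 103 |

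Every row falls outside the window. The plan speaks of "1-month post-intervention and 3-months post-intervention" without fixing a time origin, but the 3-month value is lost on either origin. If the phrase is read literally, as after the 12 weeks end, the 1-month value is lost for everyone as well and two of the three time points are empty.

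**Working backwards from 31 December 2022**

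- For 12 weeks to fit, the latest start is 31 Dec − 84 days = 8 October 2022.
- For 3 calendar months from start to fit, the latest start is about 30 September 2022.
- For 3 months after a 12-week intervention to fit, the latest start is about 8 July 2022.

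All three dates precede the opening of the window. Only a 1-month value counted from the start can fit, and only for women who start by about 30 November 2022.

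**Staggered entry**

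Assume the first week begins on 21 October; the plan does not say so. Experimental patients in the plan's example then enter from 28 October and have at most 71 − 7 = 64 days. If one week per group were enough to fill both groups, which is also an assumption, the last woman would enter on 3 November and finish 12 weeks on 26 January 2023. The conclusion does not depend on this illustration.

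**The case against.** The strongest reply is that this is a contradiction on paper and not proof that data are missing. The same section says 3-month values were collected, so the ordinary explanation is that the dates are a mislabelled recruitment period or contain a typing error. The dates are also doubtful for another reason: the document is dated 23 November 2021 yet describes collection in late 2022 in the past tense. On that view, shortfalls counted in days claim more precision than the dates can bear. The plan also names no primary time point, so losing the 3-month value need not be decisive.

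Part of this stands. The count of 0 of 48 and the empty third time point follow only if the dates are the whole collection period. The document date adds one more item to reconcile. No endpoint or time point is designated as primary.

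It does not remove the problem. The sentence says data were collected, calls the collection prospective, and leads straight into the enrolment, baseline and follow-up measurements. If the recruitment reading is the true one, the text is still wrong as written, and the date on which follow-up ends is still absent. Uncertainty about the dates is a reason to correct them, and the lack of a primary time point does not rescue an ANOVA that needs all three.

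**Conclusion.** The concern holds, and the plan must be corrected. The 71-day window cannot contain an 84-day intervention or a 3-month measurement, whichever origin is used for the 3 months. For the first possible participant the shortfall is 13 days to the end of the intervention, 21 days to 3 months from the start, and 103 days to 3 months after the end.

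As written, 0 of 48 women can have a 3-month value inside the window. This rests on two readings that the text supports: that the dates bound all data collection, and that baseline was not taken before 21 October 2022. If the dates are only the recruitment period, the measurements may be obtainable, but the plan then mislabels the window and gives no end of follow-up.

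**What to change.** Reconcile the window, the intervention length, the visit times and the document date, and replace the single date range with text along these lines:

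> Enrolment runs from 21 October 2022 to [date]. Times of 1 month and 3 months are counted from [start or end of the intervention]; for control women the origin is [date]. Data collection ends when the last enrolled woman has had her 3-month glucose measurement and has delivered. The database is not locked or analysed before then.

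If 21 October to 31 December 2022 is the enrolment window, label it so and add the later date on which follow-up is expected to end. The time origin must be stated. For the first participant, the two readings of the 3-month visit (21 January and 13 April 2023) are 82 days apart.

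The cost is an edit to the Data collection section and matching wording in the Statistical analysis section. If the stated close was really intended, it also means some further months of follow-up that the plan's own visit schedule already requires. No extra patients or procedures are needed.

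### Arms are formed by week of visit, yet the glucose model has no covariates, so a baseline imbalance biases the group main effect, and the interaction if the factor alters glucose over time

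*Combined protocol and SAP*

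**What the plan says.** **Allocation** (Study protocol, Participants): "The study objects were selected by non synchronous control". The example given sends one week's attenders to control and the next week's to the experimental arm, until enough women are enrolled. There is no randomisation, matching or stratification.

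**Size** (same section): "The target population was selected from 48 patients with gestational diabetes mellitus". The split between arms is not given.

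**Data** (SAP, Data collection): "At the time of enrollment, demographic information about the study participants was gathered", with no list of items. Before the intervention and at 1 and 3 months, "patients' glucose level indicators (FPG, 2hPG) and pregnancy outcomes were collected". Gestational age at entry, pre-pregnancy BMI, parity and previous gestational diabetes are not named anywhere.

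**Glucose analysis** (SAP, Statistical analysis): the terms are "the time effect, the main effect of the intervention, and the interaction effect of both FBG and 2hPG", measured before and at 1 and 3 months, and these "were all compared in the two groups using ANOVA". All other comparisons are t, Wilcoxon rank sum or chi-square tests. The plan has no covariate, regression or propensity method, and no rule for arms that differ at baseline.

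**The concern.** When the calendar decides who is in which arm, the comparison relies on measured baseline factors to separate the programme's effect from differences between the women who attended. This plan uses none of them apart from pre-intervention glucose, which enters as one of the repeated measures.

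Pre-intervention glucose gives partial protection. A factor that shifts a woman's glucose equally at every visit drops out of her change over time, so the interaction is safe from it. The group main effect averages over visits and keeps the shift. A factor that alters the course of glucose, so that two women with the same starting value diverge, biases the interaction as well.

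Because the plan tests both effects and gives neither priority, a reader could take either as evidence that the programme worked. At stake is whether a glucose difference can be credited to the programme or to the make-up of the arms.

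**Working it through.** The plan contains no sample-size, power or effect-size figure, so there is nothing of its own to reproduce. The calculations below show size and direction under assumptions.

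**Inputs from the documents:** 48 women; allocation by week; three glucose time points; two-sided 5% level.

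**Assumptions:** 24 per arm; a factor correlated r = 0.3 to 0.4 with glucose (up to 0.5 in step 4); a within-week intraclass correlation (ICC) for that factor of 0.05; one to four weeks per arm. None of these is in the documents.

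**Step 1. Given an imbalance, single time point.** Bias = r × imbalance. The standard error of the difference is √(2/24) = 0.289 SD. The false-positive rate comes from the noncentral t with 46 df and noncentrality bias/0.289.

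| Imbalance | r | Bias (SD) | Noncentrality | False-positive rate |
|---|---|---|---|---|
| 0.5 SD | 0.3 | 0.15 | 0.52 | 8.0% |
| 0.5 SD | 0.4 | 0.20 | 0.69 | 10.4% |
| 0.8 SD | 0.3 | 0.24 | 0.83 | 12.9% |
| 0.8 SD | 0.4 | 0.32 | 1.11 | 19.2% |

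**Step 2. How likely such an imbalance is.** The variance of the standardised difference is (2/24)(1 + (m − 1) × ICC), with m women per week.
- Independent assignment: SD 0.289; probability of more than 0.5 SD is 8.3%.
- Four weeks per arm (m = 6): variance 0.0833 × 1.25 = 0.104; probability 12.1%.
- One week per arm (m = 24): variance 0.0833 × 2.15 = 0.179; probability 23.8%.

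**Step 3. Overall rate, averaged over possible imbalances.** Clustering of the factor inflates the variance of the outcome difference by k = 1 + r²(m − 1) × ICC. The rate is then the two-sided tail of t (46 df) beyond 2.013/√k.

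| Weeks per arm | r | k | Overall rate |
|---|---|---|---|
| 4 | 0.3 | 1.0225 | 5.2% |
| 4 | 0.4 | 1.04 | 5.4% |
| 1 | 0.3 | 1.1035 | 6.2% |
| 1 | 0.4 | 1.184 | 7.1% |

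Simulation agrees to within 0.2 percentage points. With independent assignment k = 1 and the rate is 5%.

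**Step 4. The planned analysis itself.** A two-group, three-visit ANOVA was simulated with no treatment effect, 24 per arm, within-patient correlation 0.5 and 5,000 runs per scenario. The factor's effect ran from 0.3 to 0.5, either constant across visits or growing from zero at baseline.

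| Factor's effect | Imbalance | Bias, group main effect (SD) | False-positive rate, main effect | Bias, change to 3 months (SD) | False-positive rate, interaction |
|---|---|---|---|---|---|
| Constant | 0.25 SD | 0.08 to 0.12 | 5.7 to 7.2% | about 0 | about 5% |
| Constant | 0.5 SD | 0.15 to 0.25 | 9.4 to 17.0% | about 0 | about 5% |
| Growing | 0.25 SD | 0.04 to 0.06 | 4.5 to 5.8% | 0.07 to 0.12 | 5.7 to 6.7% |
| Growing | 0.5 SD | 0.08 to 0.13 | 6.3 to 9.1% | 0.15 to 0.25 | 8.0 to 12.3% |

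With the factor in the model, the rate was 4.3 to 5.7% in every scenario, both for the group effect and for the change from baseline to 3 months.

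**The case against.** Five arguments can be made on the other side.

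1. **The larger error rates are conditional.** The 8 to 10% applies only once a 0.5 SD imbalance has occurred. If weeks behaved like random assignment, the unadjusted test would hold 5% overall. This stands, and step 3 gives the modest overall figures. A systematic difference between weeks could do more, but the documents point to none.

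2. **Pre-intervention glucose is already in the model.** A reader might infer that any imbalance passes straight into the glucose result. The plan does not support that: a factor with a constant effect cancels from the interaction. What stands is the bias in the group main effect, which the plan also tests, and in the interaction for factors that change the course of glucose.

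3. **Demographics may be shorthand.** In so brief a plan the term could cover BMI, parity and gestational age, so the text does not show that these went unrecorded. Nor does it follow that they could never be adjusted for: if routine antenatal notes hold them, they can be retrieved. What would be lost is choosing them in advance. Even if recorded, they are not in the model.

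4. **The inputs are assumed.** The correlations and the ICC have no source in the documents. That is correct, and the results are shown as ranges.

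5. **Covariates do not replace randomisation.** True. They deal only with measured differences, and which two to choose is a judgement.

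**Conclusion.** The point holds in a limited form. The plan compares non-randomised arms with no adjustment for any prognostic factor beyond carrying pre-intervention glucose as a repeated measure. An imbalance in gestational age, pre-pregnancy BMI or previous gestational diabetes, taken here to be related to glucose, biases the group main effect. It biases the interaction only if the factor affects glucose over follow-up.

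Under the stated assumptions, a 0.5 SD imbalance matters (bias 0.15 to 0.20 SD, false-positive rate 8 to 10% at a single time point). The overall inflation from one such factor is small: about 5.2 to 5.4% with four weeks per arm and 6.2 to 7.1% with one week per arm. It would be larger if weeks differ systematically.

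The documents do not support saying that the trial's false-positive rate is 8 to 10%, or that the factors are definitely missing. Nor would adjustment make the arms comparable in every respect. This is an inexpensive improvement to make, not a flaw that invalidates the comparison.

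**What to change.** - **Record at enrolment, from the antenatal record:** gestational age at entry, pre-pregnancy weight and height, parity and previous gestational diabetes. List them in the Data collection section.
- **Adjust as fixed in advance.** Possible SAP wording: FPG and 2hPG will each be analysed by repeated-measures ANOVA with group, time and group-by-time, and with gestational age at entry and pre-pregnancy BMI as covariates, each with its interaction with time. The covariate-by-time terms are needed because a covariate with only a constant effect does not correct the interaction.
- **Report standardised differences between arms** for all baseline factors. P values are a poor guide to comparability here: with 24 per arm, a t-test has power 0.40 for a 0.5 SD difference, so it misses 60% of them. The plan does not say that its t-tests are meant for this purpose.
- **State the limitation** that unmeasured and week-level differences remain after adjustment.

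The cost is a few form fields, which routine notes are assumed to hold, and a sentence or two in the SAP. Two covariates use 2 of the 46 between-patient degrees of freedom (48 − 2). Their interactions with time use 2 × 2 = 4 of the 92 within-patient ones (46 × 2). With 48 women the model can support only a few covariates, so the list should stay short.
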